Study Design: The proposed 12 month vanguard study will be a randomized controlled trial of patients training for home hemodialysis. The primary outcome for the proposed study is feasibility to recruit to the two different needle cannulation arms and coordination of the study centres. Additionally, demographic data will be retrospectively collected on patients who trained to do home hemodialysis, but were not eligible for the study to help explain recruitment challenges.

Patient Population:

Inclusion Criteria

The following inclusion criteria will be used: 1. Adult patients > 18 years old, 2. Training for home hemodialysis using self cannulation, 3. Returning to train to use an AVF (i.e. went home using a CVC or another access that has failed), 4. Able to give informed

consent, 5. Arteriovenous fistula (patients with segments of grafts that are not at the sites of needle insertion may be included), and 6. Life expectancy of greater than 12 months

Exclusion Criteria

The following exclusion criteria will be used: 1. Potential to be lost from the program within 12 months of training (planned living donor transplant, transfer to PD or move from training centre catchment area), 2. Short segments or aneurysms within the AVF that the attending nephrologist believes require buttonhole cannulation, 3. Mechanical heart valves, 4. Patients who require intradermal lidocaine for needle insertion

Study Overview

After obtaining informed consent, basic demographic data will be collected including age, sex, cause of end stage renal disease, arteriovenous access history [date of creation, previous interventions (angioplasties, surgical revisions), previous infections] and comorbidity information to calculate the Charlson comorbidity index. Demographic data will also be retrospectively collected on patients who were training for home hemodialysis but were not eligible to participate in the study.

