All eligible patients will be randomized to either step ladder or buttonhole cannulation technique for needle insertion. Randomization will be determined via a computer generated randomization code with stratification by site and AVF type (incident vs. prevalent). The group assignment will be kept in sealed opaque envelopes and provided to sites via the coordinating centre at the time of study consent. Only the investigators will be aware of the training time as an objective of the study as the intervention cannot be blinded and the outcome is potentially influenced by factors other than needle insertion technique. For consent and the remainder of the health team; the purpose of the study will be to determine feasibility, infection rates and other complications associated with the two different needle insertion techniques. Each Research Ethics Board will need to approve that one of the study objectives will be concealed.

Data collection forms will be developed with the assistance of the Ottawa Hospital Methods Centre and pilot tested at 2 sites (Ottawa and University Health Network) prior to the creation of an electronic data capture form to be used by all participating sites. The amount of time required to consent patients, complete the case report forms and follow each patient for the complication outcomes will be documented at these two sites so that this data can be used to inform the definitive trial budget.

After ensuring that the case report forms and access documentation tool are useable and all necessary information is being collected, the remaining programs will begin to recruit patients. Each program will be responsible for keeping a log of all patients who are training for home hemodialysis and the proportion of patients who are candidates for the study. Of the patients that are candidates for the study, the number of patients who are randomized to the study will be tracked. Reasons for not participating in the study for all potential candidates will be documented and reviewed at quarterly meetings. If themes are identified that are limiting enrollment, solutions will be proposed by the investigators and implemented if possible.

Needle Insertion Techniques

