Any additional days of training and any days required for re-training will be included in the overall cost. Any differences in the cost of the blunt versus sharp needles and the mupirocin for buttonhole cannulation will be included in the overall cost. Treatment for infection including antibiotics and hospitalizations will be included and costed according to established principles. Similarly, the cost associated with any required angiogram (leading to an angioplasty), angioplasty or surgical revision will be included.

Visual Analogue Scale – Pain with Needling (Appendix 1)

All patients will continue (or start) with the step ladder insertion technique for the first 2 to 3 days at which time they will use the validated 10 cm visual analogue scale to rate the pain they experience with needle insertion. The visual analogue scale will be repeated at 2 additional time points – at the end of training and approximately 2 months after graduating home hemodialysis training. As many of the programs train 3 days per week, the additional time point is to capture the potential differences in perceived needling pain with increased frequency of needle insertion. It is unclear if buttonholes are easier to maintain when used more than 3 days per week as this may be associated with less pain on needle insertion. Topical anesthetics will not be withheld during assessments of pain with the visual analogue scale but the requirement for use will be documented.

Sample Size Calculation

There are a limited number of patients who start home HD each year in Canada. If we are unable to get at least 70% enrollment in the pilot study – it is very unlikely that we will be able to successfully undertake a study with a larger sample size. For the purposes of the feasibility pilot, the first 2 centres (Ottawa and University Health Network) will recruit participants for 18 months with the remaining centre's participating for 12 months. All patients who are eligible for the study will be approached for recruitment. Our goal is to demonstrate that we can successfully recruit. For the definitive study to explore the differences in training time between the two needle cannulation techniques: The mean number of training days for patients with an AVF in the FHN studies was 27.7 with a standard deviation of 10.4 (20). This was reduced by 5 days for patients using a central venous catheter. Assuming that a buttonhole cannulation would

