have a similar impact on training time, 69 patients per groups would give us 80% power to detect this difference. The number required in the trial increases to 107 if the difference is 4 days.

Analysis

For the purposes of the pilot study, basic demographic characteristics of the included and excluded patients will be described using appropriate descriptive statistics. This data will be retrospectively collected on patients who were not enrolled in the study. The percent of qualified patients enrolled in the study for the pilot study to be successful will be $\geq 70\%$. The secondary outcomes will be analyzed on an intent to treat basis upon completion of the main study assuming that this trial is feasible. The comparison of mean training times will be done with an un-paired t-test. A linear regression analysis will also be undertaken to examine predictors of training time including age, sex and Charlson comorbidity score in addition to needle insertion technique. Any differences in pain scores depending of frequency of cannulation will be explored within cannulation techniques. If no differences exist by frequency of cannulation, the data will be combined and the median pain scores will be assessed with a Wilcoxon rank sum test. The different types of complications and costs will be categorized and the overall mean differences will be assessed with an unpaired t-test. Any differences in outcomes by frequency of cannulation will also be explored within each of the secondary outcomes.

For patients who return to train on cannulation technique (started home HD with a CVC or other access that failed); their data will not be included in overall training time but all other study outcomes will be tracked and included in the analysis infections and complications.

The retrospectively collected demographic data will be analyzed in order to describe the patient population.

Data Safety Monitoring Board

Drs. [name] and [name] in addition to [name] (vascular access coordinator) have agreed to monitor the outcomes of this study. If we detect infection rates that are comparable to or greater to the benchmark for central venous catheters as adopted by the Ottawa Hospital - the study will be stopped (external benchmark bacteremia rate of 4.6 per 100 patient months, Nephrology News and Issues 2005, 37-43)

Study Investigators

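### Cost analysis does not say whether returning patients and their training days count; if they do, an unadjusted t-test may lose precision that a new/returning term would recover

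*Combined protocol and SAP*

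**What the plan says.** All references are to the combined protocol and SAP.

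- **Inclusion Criteria, item 3** admits patients who return to train on a fistula after going home with a catheter or another access that failed.
- **Analysis** takes these patients out of one outcome and keeps them for the others: "their data will not be included in overall training time but all other study outcomes will be tracked and included". The full ending is narrower: "all other study outcomes will be tracked and included in the analysis infections and complications". Cost is not named, and no reason is given for the training-time exclusion.
- **Costs of Vascular Access** says: "Any additional days of training and any days required for re-training will be included in the overall cost". It makes no exception for returning patients and does not define which days are additional. The other cost items are needles, mupirocin, treatment of infection (including hospital stays), angiograms, angioplasty and surgical revision.
- **Analysis** gives the cost test: "The different types of complications and costs will be categorized and the overall mean differences will be assessed with an unpaired t-test". The only regression is for another outcome: "A linear regression analysis will also be undertaken to examine predictors of training time including age, sex and Charlson comorbidity score", with needle technique as the further term. It has no new/returning term.
- **Study Overview** stratifies randomisation by site and by incident or prevalent fistula, not by new or returning status.
- **Analysis** also states that secondary outcomes are analysed by intention to treat once the main study is complete.

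**The concern.** Cost is in the trial title and is a secondary objective. The plan treats returning patients separately for training time, yet it does not say how they enter an outcome that is partly built from training days. There are two readings, and each has a drawback.

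- **Returning patients are in the cost comparison.** Someone already established on home dialysis who returns to learn cannulation may need fewer days than someone learning home dialysis from the start. If those days are costed, the t-test carries the between-type difference as unexplained variation, and a chance imbalance in the share of returning patients goes uncorrected.
- **Returning patients are out of the cost comparison.** Randomised patients are then dropped, which conflicts with the intention-to-treat statement.

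Two analysts could follow the text faithfully and report different cost results from the same data. Under Study Investigators, pilot data may be kept for the definitive trial, so the rule should be fixed before outcomes are seen.

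**Working it through.** **1. The plan's own figure.** The inputs are from Sample Size Calculation: standard deviation (SD) 10.4 days, difference 5 days, power 80%. Two-sided 5% and 1:1 allocation are not stated; I assume them because they reproduce the result.

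n per group = 2 × (1.960 + 0.842)² × 10.4² / 5² = 2 × 7.85 × 108.16 / 25 = 67.9. The t-test version gives 68.9, so the stated 69 per group reproduces. This figure is for training time. The plan states no sample size, effect or SD for cost.

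**2. Assumptions that the documents do not supply.**
- p, the share of returning patients: 5% to 30%.
- g, the gap in mean training days between new and returning patients: 5 to 20 days.
- S, the SD of all other cost items in training-day equivalents: 0, 10.4 or 20.8.

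It is also assumed that returning patients' training days are costed, and that the within-type SD of training days is 10.4.

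**3. Formula.** A model with a new/returning term leaves residual variance 10.4² + S². The unadjusted t-test leaves 10.4² + S² + p(1−p)g². Hence

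SE ratio (unadjusted to adjusted) = √[1 + p(1−p)g² / (10.4² + S²)].

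The denominators are 108.16 (S = 0), 216.32 (S = 10.4) and 540.80 (S = 20.8).

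| p, g | p(1−p)g² | SE inflation, S = 0 | S = 10.4 | S = 20.8 |
|---|---|---|---|---|
| 5%, 5 days | 1.19 | 0.5% | 0.3% | 0.1% |
| 10%, 10 days | 9 | 4.1% | 2.1% | 0.8% |
| 20%, 15 days | 36 | 15.4% | 8.0% | 3.3% |
| 30%, 20 days | 84 | 33.3% | 17.8% | 7.5% |

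For the third row with S = 0: √(1 + 36/108.16) = √1.333 = 1.154.

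**4. The same in power terms, for the training-day component only.** With S = 0, a 5-day difference and 69 per arm, the normal approximation gives 80.6% with the term. Without it, power is 80.2%, 77.4%, 68.7% and 56.3% down the four rows.

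**5. Simulation check** (2,000 runs, 69 per arm, true difference −5 days, S = 0). Over the four settings tried, the mean unadjusted estimate ran from −4.94 to −5.06, so there is no bias. At 20% and 15 days, power was 70.2% unadjusted and 81.0% adjusted. At 30% and 20 days it was 55.4% and 79.0%.

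**The case against.** The strongest reply is that the mechanism may not operate at all. Costs of Vascular Access speaks of additional days and of re-training, not of every training day for every patient. Summary and Conclusions notes that reimbursed training days are fixed, so additional may mean days beyond a standard course. Re-training may mean re-trains for needling difficulty (Secondary Objectives) or a return to form a new buttonhole (Time to Train), rather than a returning patient's first fistula course. On that reading the gap g does not enter cost as modelled. This stands: the loss is conditional, and the plan has to settle the condition.

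A reader might also infer three stronger things that the documents do not support.

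- **That the plan regards returning patients as not comparable.** This is a natural guess, but no reason for the exclusion is given.
- **That power for cost falls from about 80% to 68% or 69%.** That borrows the SD, effect and sample size for training time and sets the variance of hospital stays, interventions and supplies to zero. With S = 20.8, the 20% and 15-day case inflates the SE by 3.3%. A comparison with 80% power when adjusted would then have about 77%: (1.960 + 0.842)/1.033 − 1.960 = 0.753, and Φ(0.753) = 0.774.
- **That the t-test is biased or invalid.** Status precedes randomisation, and the simulation shows no bias. Adjustment is an efficiency choice.

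Finally, cost is secondary and is analysed only if the main study goes ahead, so no feasibility conclusion depends on this.

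**Conclusion.** The point holds as a gap in specification with a possible loss of precision in a secondary outcome. It is certain from the text that returning patients are randomised, that their place in the cost analysis is not stated clearly, and that neither the cost test nor the stratification takes account of new/returning status.

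The size is not fixed by the documents. It runs from negligible (few returning patients, a small gap, or cost driven mainly by hospital stays and interventions) to material (many returning patients, a large gap, and cost driven mainly by training days). The upper figures need both large assumed inputs and little variation from other cost items. If returning patients' training days are not costed, this route to lost precision disappears and the need for clarification remains. If the patients themselves are left out of cost, the problem is a departure from intention to treat.

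**What to change.** In the Analysis section:

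1. State that all randomised patients, including those returning to train on a fistula, are in the cost comparison in the arm to which they were assigned.
2. State whether returning patients' fistula-training days are costed, and define additional and re-training days so that the rule can be applied to them.
3. Replace the unpaired t-test for cost with a linear model of cost on arm and new/returning status. The arm coefficient is still a difference in mean cost.
4. Fix the status at consent, so that a participant who later goes home on a catheter and returns is not reclassified after randomisation.

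This takes a few sentences and one degree of freedom, with negligible loss if status turns out not to matter. No new data are needed, because status is already required for eligibility and for the training-time exclusion. Randomisation and the feasibility criterion stay as they are.

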The insertion of needles into an AVF has traditionally been via the step ladder or continuous site rotation technique. However, the buttonhole method was introduced in the 1970's in an attempt to address some of the challenging issues associated with AVF accesses.¹⁹ In the buttonhole technique, a constant site is used for needle placement that ultimately results in a fibrous tract. Once the tract has formed blunt needles can be used instead of sharp needles for each treatment. The presence of a tract may simplify the needle insertion technique and lead to enhanced patient confidence with needle placement. Although no studies have reported training times in association with needle insertion technique, Pipkin et al have demonstrated a mean reduction in training time for home hemodialysis patients of 5 days when a central venous catheter was used for an access compared to an AVF.²⁰ It is reasonable to assume that well established buttonholes may also lead to a similar reduction in training times. Other reported benefits of buttonhole cannulation include less painful needling,²¹⁻²⁴ fewer needle infiltrations,^{19,24,25} fewer interventions²⁶ and a reduction in aneurysm size.²³ While earlier studies demonstrated a reduction in pain with buttonhole needling, more recent studies show either no reduction in pain,^{27,28} or even an increase in pain.²⁶ However, the effect of frequency of use on the maintenance of the buttonhole and the perception of pain has not been explored. Importantly however, there has also been increasing concern about the potential for an increased risk of infection using the buttonhole cannulation technique with estimates of *Staphylococcus aureus* (*S. aureus*) bacteremia for patients receiving high dose dialysis between 0.15 to 0.60 episodes per 1000 patient-days across 4 studies.²⁹⁻³² In an indirect comparison between high dose home hemodialysis with buttonhole cannulation versus in-centre conventional hemodialysis with rope-ladder cannulation, the relative risk for bacteremia ranged between 30 to 120. Importantly, *S. aureus* bacteremia was associated with devastating consequences, including septic arthritis, septic pulmonary emboli, vertebral osteomyelitis, and death in a single centre's experience.³³ In one small study, the risk of infection associated with buttonhole

cannulation was prevented by the application of topical mupirocin at the buttonhole sites post hemodialysis.

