The home hemodialysis run sheet will be modified so that the patient can record any instances of hematoma formation (obvious bruising at the arteriovenous site that occurs at the time of needle insertion or withdrawal) or missed needle sticks (unable to use the needle for dialysis). For buttonhole cannulation, the need to use a sharp needle instead of the usual blunt needle will be considered a missed needle stick even if a separate needle insertion site is not required. Patients will be instructed to come to the home dialysis unit if they notice any localized signs of infection over the AVF including heat, erythema, purulent drainage or induration. A swab will be sent for gram stain, culture and sensitivity; infection will be diagnosed if neutrophils are present with cultured bacteria. Additionally patients will be asked to contact the unit and present themselves to the nearest emergency department if they develop fever, chills and/or hypotension with the hemodialysis treatment. An access related bacteremia will be defined using CDC criteria

(at least one of the following: 1) Patient has a recognized pathogen cultured from one or more blood cultures and the pathogen is not related to an infection at another site or 2) patient has fever, chills, and/or hypotension as well as positive laboratory cultures from two or more blood samples drawn on separate occasions which are not related to infection at another site and do not reflect contamination). As the most common pathogen is *S. aureus*, all patients with *S. aureus* related bacteremia will be monitored for metastatic complications including an echocardiogram at the discretion of the treatment center. Access interventions including angioplasties and surgical revisions will be documented. The vascular access coordinator, or similarly trained individual, will document the presence of aneurysms at the start and completion of the study. A standardized tool for assessment of the number of aneurysms, size and potential risk of rupture (thinness of skin) will be developed with the assistance of skilled vascular access coordinators (access documentation tool).

Costs of Vascular Access

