The definitive study will be part of the Canadian Intensive Hemodialysis Physician Group with representation from across Canada. The vanguard study will be collecting information from sites in Ottawa ([name]), Toronto (Drs. [name], [name] and [name]), Calgary ([name]) and Vancouver ([name]). All investigators have experience in high dose hemodialysis and clinical investigation. [name] has additional experience in economic analysis and [name] has just published a study of buttonhole versus stepladder cannulation in the in-centre conventional hemodialysis population. All

together, these sites train approximately 70 patients for high dose hemodialysis per year which will provide an adequate number of participants to ensure the success of this pilot study within the 2 years allotted for this grant. If no changes to the protocol are required, feasibility clearly established and sample size achievable, the pilot study data will be retained for the definitive trial.

Appendix 2

References:

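### Must the protocol state whether the 4.6 per 100 patient-months stopping benchmark applies by arm or pooled, and when it is checked?

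*Combined protocol and SAP*

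**What the plan says.** The Data Safety Monitoring Board section names three monitors who "have agreed to monitor the outcomes of this study". The stopping rule is a single sentence: the study will be stopped "If we detect infection rates that are comparable to or greater to the benchmark for central venous catheters as adopted by the Ottawa Hospital", with the benchmark in brackets as an "external benchmark bacteremia rate of 4.6 per 100 patient months". The section gives no arm basis, review dates, minimum exposure or margin for the word comparable.

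Three other places bear on it:

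- **Study Overview, meetings.** The only schedule in the document is for reasons for non-participation, which "will be documented and reviewed at quarterly meetings". It does not cover infection rates.
- **Study Overview, stated purpose.** The purpose given for consent and to the wider health team includes infection rates and other complications associated with the two needling techniques.
- **AVF Access Complications.** Local infection and bacteremia are defined separately. For a swab, "infection will be diagnosed if neutrophils are present with cultured bacteria"; and "An access related bacteremia will be defined using CDC criteria".

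**The concern.** The rule is worded as mandatory, so its unstated parts look important. There are three apparent weaknesses.

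1. **Early on, it is easily met.** When little exposure has accrued, one bacteremia gives a crude rate above 4.6 per 100 patient-months, although one event says almost nothing about the true rate. A stop at that point would also end the feasibility assessment, which is the primary objective.
2. **Later, a pooled rate could hide an excess.** The background section expects more infection with buttonholes. If the rate is pooled, a low step-ladder rate dilutes a high buttonhole rate, and the two readings could give opposite decisions on the same data.
3. **The event type is loosely named.** The trigger speaks of infection rates, but the benchmark in brackets is for bacteremia only.

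**Working it through.** **Inputs from the document.** The benchmark is b = 4.6 per 100 patient-months (0.046 per patient-month). It is an adopted external value, so there is no derivation to reproduce. Background *S. aureus* bacteremia in high-dose patients is "between 0.15 to 0.60 episodes per 1000 patient-days across 4 studies". At 30.44 days per month that is 0.15 × 30.44/10 = 0.457 and 0.60 × 30.44/10 = 1.826 per 100 patient-months. Both are below b, but they cover *S. aureus* only. On size, "these sites train approximately 70 patients for high dose hemodialysis per year".

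**Assumptions.** Equal patient-time per arm; 18 to 70 patients in total; uniform 12-month accrual; 12 months' follow-up each; *comparable or greater* read as 4.6 or more; step-ladder rate 1/30 or 1/2 of the buttonhole rate. The 1/30 is the lower end of the indirect in-centre comparison in the background.

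**Step 1: one event.** 1/0.046 = 21.74 patient-months. One event in that exposure gives 4.6 per 100 with an exact 95% interval of 0.12 to 25.6. The chance of at least one event in 21.74 patient-months is 1 − exp(−rate × 21.74):

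- at 0.457 per 100: 1 − exp(−0.0993) = 9.4%
- at 1.826 per 100: 1 − exp(−0.397) = 32.8%

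The problem fades as exposure grows. The count needed is b × T rounded up: 3 events at 50 patient-months, 5 at 100, 10 at 200. Timing matters: a check at every event over 200 patient-months crosses about 10% or 40% of the time at the two background rates, against 0.01% or 3.8% for a single look at 100.

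**Step 2: pooling at a single check.** With equal exposure and step-ladder/buttonhole ratio r, the pooled rate equals b when the buttonhole rate is 9.2/(1 + r):

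- r = 0: 9.2 (2.0 times the benchmark)
- r = 1/30: 8.90
- r = 1/2: 6.13 (1.33 times)

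For example, 14 events against 0 in 400 patient-months is 14/400 = 3.5 pooled, but 14/200 = 7.0 in the buttonhole arm (95% interval 3.8 to 11.7).

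Such data lie far from the document's own figures. At 1.826 per 100, 200 buttonhole patient-months yield about 3.65 events, and the chance of 14 or more is about 3 in 100,000.

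**Step 3: repeated checks.** The table gives the simulated chance of ever crossing with quarterly checks, for 18, 40 and 70 patients.

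| True buttonhole rate | Step-ladder | Pooled | By arm |
|---|---|---|---|
| 9.0 per 100 | zero | 77%, 81%, 80% | nearly always (98% or more) |
| 4.6 per 100 | 1/30 | 35%, 34%, 25% | 76%, 79%, 83% (buttonhole arm) |
| 1.826 per 100 | 1/30 | 11%, 12%, 6% | 30%, 25%, 26% (either arm) |
| 1.826 per 100 | 1/2 | 17%, 18%, 11% | 39%, 32%, 34% (either arm) |

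So a pooled rule checked quarterly would still usually be met at nearly twice the benchmark. By-arm application detects a benchmark-level rate far better, but it is crossed about two to four times as often at a rate below the benchmark. One-event stops contribute heavily: for the buttonhole arm at 1.826, quarterly crossing is 24% to 29% in all, and crossing on exactly one event is 15% to 21%.

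**Step 4: a minimum exposure.** The obvious curb on one-event stops is to require some exposure first. With 50 patient-months as an illustration, quarterly buttonhole-arm crossing at 1.826 falls from 24%–29% to 6%–10%. Crossing at a true benchmark rate also falls, from 76%–83% to 63%–75%. That loosens a safety rule.

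**The case for a change.** The strongest case for a change is that the text says the study will be stopped, leaves the basis open, and the basis matters. At a true benchmark buttonhole rate with step-ladder at 1/30, quarterly checks cross 76%–83% of the time by arm and 25%–35% pooled. The trial exists to compare two techniques expected to differ in infection, bacteremia can have grave consequences, and a clarifying paragraph needs no extra data.

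Much of this stands: the omission, the arithmetic, and the fact that the quarterly meetings do not supply the missing schedule. Three points weigh against amending the plan.

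- **The rule is not purely mechanical.** The word comparable has no numerical margin, so the monitors must interpret it. Monitors looking at one early event, or at events confined to one arm, would see what they were looking at.
- **The text already leans one way.** The Study Overview links infection rates to the two techniques, and the bracketed benchmark names bacteremia. Neither settles the matter, but both point to a by-technique bacteremia rate.
- **The remedy worsens part of the complaint.** Fixing the rule by arm makes early one-event stops more frequent, and curbing those with a minimum exposure weakens protection. Asking for stated review times without naming any leaves the choice where it is now.

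**Conclusion.** No change to the plan is needed. The arm basis, review times and event wording are unwritten monitoring details that the named monitors can sensibly settle. The choice between by-arm and pooled is a fair trade-off: about 76%–83% against 25%–35% crossing at a true benchmark buttonhole rate (step-ladder 1/30), and about 25%–39% against 6%–18% at 0.60 per 1000 patient-days (step-ladder 1/30 to 1/2). The dilution worry is real at a single check (a ceiling of 9.2 with no step-ladder events, 6.1 with half the rate), but repeated pooled quarterly checks would still cross about 77%–81% of the time at a true rate of 9.0.

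The omission and the 21.7 patient-month figure are certain. The crossing probabilities rest on assumed enrolment, accrual, equal exposure, quarterly checks and step-ladder ratios, and on a background range for *S. aureus* only, so all-pathogen rates could be higher.
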